11.3 Vital Signs (Including Height and Weight)

Raw (actual) values for vital signs (e.g., systolic and diastolic blood pressure, pulse rate, and body temperature) and their changes from baseline at each post-baseline assessment time point will be summarized.

Vital sign values will be considered PCI if they meet both the observed value criteria and the change from baseline criteria listed in [Table 5](#). The number and percentage of subjects with PCI post-baseline values at each scheduled time point will be tabulated. The percentages will be calculated relative to the number of subjects with baseline and at least 1 post-baseline assessment. The numerator is the total number of subjects with at least 1 PCI post-baseline vital sign value. A supportive listing of subjects with post-baseline PCI values will be provided including the subject number, baseline, and post-baseline PCI values.

All vital signs data (including height and weight) will be listed, and listing(s) will be based on the Safety Analysis Set.

Table 5: Criteria for Potentially Clinically Significant Vital Signs

Parameter	Classification	Criteria
Systolic blood pressure (mm Hg)	HIGH and INCREASE	≥ 140 and increase of ≥ 20 from baseline value
	LOW and DECREASE	≤ 90 and decrease of ≥ 20 from baseline value
Diastolic blood pressure (mm Hg)	HIGH and INCREASE	≥ 90 and increase of ≥ 15 from baseline value
	LOW and DECREASE	≤ 50 and decrease of ≥ 15 from baseline value
Pulse rate (bpm)	HIGH and INCREASE	≥ 100 and increase of > 15 from baseline value
	LOW and DECREASE	≤ 45 and decrease of > 15 from baseline value
Temperature	HIGH	$> 38.3^\circ\text{C}$ or $> 100.9^\circ\text{F}$
	LOW	$< 35^\circ\text{C}$ or $< 95^\circ\text{F}$

11.4 Electrocardiogram (ECG)

Raw (actual) values for ECG variables (e.g., heart rate, RR interval, PR interval, QRS interval, QT interval, and QTc interval) and their changes from baseline at each post-baseline assessment time point will be presented. QTc interval will be calculated using both Bazett ($QTcB=QT/(RR)^{1/2}$) and Fridericia ($QTcF=QT/(RR)^{1/3}$) corrections; and if RR is not available, then 60/heart rate will be used in the correction formula. Electrocardiogram interpretation, per the investigator, will be summarized by assessment time point for all scheduled assessments. In addition, a shift table from baseline to each post-baseline assessment time point for categorical ECG results will be provided.

Subject's baseline ECG is defined as the single ECG collected predose on Day 1 (or unscheduled ECG collected after the scheduled predose timepoint but prior to the administration of investigational product).

Electrocardiogram variable values will be considered PCI if they meet or exceed the upper limit values listed in [Table 6](#). The number and percentage of subjects with post-baseline PCI values at each scheduled time point will be tabulated. The percentages will be calculated relative to the number of subjects with available non-PCI baseline and at least 1 post-baseline assessment. The numerator is the total number of subjects with at least 1 PCI post-baseline ECG value. A listing of all subjects with post-baseline PCI values will be provided including the subject number, baseline, and post-baseline PCI values.

All ECG data will be listed, and listing will be based on the Safety Analysis Set. Listings of ECG data, including interpretation by individual subject, will also be produced.

Table 6: Criteria for Potentially Clinically Important ECG Values

Parameter	Classification	Criteria
Overall Evaluation	ABNORMAL	Overall Evaluation is ABNORMAL
Heart rate (bpm)	HIGH and INCREASE	≥ 100 and increase of > 15 from baseline value
	LOW and DECREASE	≤ 45 and decrease of > 15 from baseline value
PR interval (msec)	HIGH and INCREASE	≥ 200 and increase of ≥ 20 from baseline value
QRS interval (msec)	HIGH	≥ 120
QTc interval (men) (msec)	HIGH	> 430 and increase from baseline value > 30
QTc interval (women) (msec)	HIGH	> 450 and increase from baseline value > 30

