### Single ECG Recordings – (Day 1 through Day 112)

One complete recording, including a 10-second rhythm strip, should be taken at all time points except at the initial Screening Visit and at check in to the CRC on Day -1. It should be immediately assessed as a valid recording and if not valid, it should be repeated. Invalid recordings will not be entered in the CRF.

When a single ECG recording is performed at each time point, the ECG collected predose on Day 1 will serve as the subject's baseline ECG.

To ensure safety of the subjects, a qualified individual at the investigator site will make comparisons to baseline measurements.

If the QTcF interval (calculated online on site) is increased by >45msec from the baseline or an absolute QTcF value is >500msec for any scheduled ECG, then 2 additional ECGs will be collected, approximately 2-4 minutes apart, to confirm the original measurement. If either of the QTcF values from these repeated ECGs remains above the threshold value (>4 msec from the baseline; or is >500msec), then a single ECG must be repeated at least hourly until QTcF values from 2 successive ECGs fall below the threshold value that triggered the repeat measurement.

If QTcF values remain above 500msec (or >45msec from the baseline) for >4 hours (or sooner at the discretion of the investigator) or QTcF intervals get progressively longer, the subject should undergo continuous ECG monitoring. A cardiologist should be consulted if QTcF intervals do not return to <500msec (or to <45msec above the baseline) after 8 hours of monitoring (or sooner at the discretion of the investigator).

If a machine-read QTcF/QTcB value is prolonged, as defined above, repeat measurements may not be necessary if a qualified physician's interpretation determines that the QTcF/QTcB values are in the acceptable range.

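### The SAP's QTc row in Table 6 can miss a QTcF rise above 45 msec that the protocol treats as needing confirmation; the gap affects flagging and counting only

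*SAP*

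**What the plan says.** SAP 11.4 sets the reporting screen. It introduces Table 6 with "Electrocardiogram variable values will be considered PCI if they meet or exceed the upper limit values listed in" that table. The QTc entry for men is "> 430 and increase from baseline value > 30" and for women "> 450 and increase from baseline value > 30", so the absolute limit and the rise must both be met. There is no QTc row based on change alone and none at 500 msec. The SAP derives both QTcB and QTcF, but the Table 6 rows say only QTc. Another row counts an ECG when "Overall Evaluation is ABNORMAL".

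Protocol 7.2.2.9 (Single ECG Recordings) sets the on-site rule. Two further ECGs are taken if QTcF "is increased by >45msec from the baseline or an absolute QTcF value is >500msec for any scheduled ECG". Either condition is enough, and the measure is QTcF only.

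The baselines agree. The protocol says "the ECG collected predose on Day 1 will serve as the" subject's baseline; the SAP says "baseline ECG is defined as the single ECG collected predose on Day 1", allowing for a later unscheduled predose recording.

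Neither document links the PCI criteria to the protocol trigger.

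**The concern.** One rule joins its two conditions with AND, the other with OR. An ECG can therefore satisfy the protocol's change condition without reaching the SAP's absolute limit. The protocol names ECG change from baseline as a safety endpoint, and Protocol 9.9 plans to summarize or list potentially clinically important findings. A subject could have repeat ECGs, then hourly ones, under the protocol while the QTc row of table 14.3.6.4 reads zero and listing 16.2.8.3.2 omits that subject. At stake is whether the PCI outputs count the trial's own QTcF trigger.

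**Working it through.** **Inputs.**
- SAP Table 6: PCI if QTc > L and rise > 30 msec, with L = 430 (men) or 450 (women).
- Protocol 7.2.2.9: trigger if QTcF rise > 45 msec or QTcF > 500 msec.
- Protocol exclusion 9: QTc > 450 (men) or > 470 (women) at Screening or Day -1. There is no lower limit.

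The plan states no figure to reproduce; this is a comparison of two rules.

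**Rise arm.** A rise above 45 already exceeds 30, so the QTc row fails only if the post-dose value is at or below L. That requires baseline + 45 < L:
- men: baseline < 430 − 45 = 385
- women: baseline < 450 − 45 = 405

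| Sex | Baseline | Post-dose | Rise | Protocol trigger | QTc row |
|---|---|---|---|---|---|
| Man | 380 | 428 | 48 | met | not met |
| Man | 384 | 430 | 46 | met | not met |
| Man | 385 | 431 | 46 | met | met |
| Woman | 400 | 448 | 48 | met | not met |
| Woman | 404 | 450 | 46 | met | not met |
| Woman | 405 | 451 | 46 | met | met |

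From a baseline of 360, rises of up to 430 − 360 = 70 msec (men) or 450 − 360 = 90 msec (women) stay outside the row. Reading the SAP's introductory sentence as at-or-above moves these boundaries by only 1 msec.

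**500 msec arm.** A value above 500 escapes the row only if the rise is 30 or less, so baseline must exceed 500 − 30 = 470. Exclusion 9 makes such a Day 1 baseline unlikely.

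**Choice of correction.** From the SAP formulas, QTcB = QTcF × RR^(−1/6). Assume a steady 65 bpm: RR = 60/65 = 0.923 s and the factor is 1.0134. The man's 380 to 428 becomes QTcB 385 to 434 (+49), and the woman's 400 to 448 becomes 405 to 454 (+49). Both would be flagged if the row also applied to QTcB. At 60 bpm RR = 1, the two corrections coincide and neither is flagged.

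**How many subjects could be affected.** The documents give no baseline QTcF distribution. Assume it is normal, with mean 380–420 and SD 15–20 msec. The share with a low enough baseline is Φ((384.5 − mean)/SD) for men and Φ((404.5 − mean)/SD) for women:
- men: from Φ((384.5 − 420)/15) = 0.01 to Φ((384.5 − 380)/15) = 0.62
- women: from Φ((404.5 − 420)/15) = 0.15 to Φ((404.5 − 380)/15) = 0.95

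This is the share in whom a miss is possible, not the share missed. The documents contain nothing on the chance of a rise above 45 msec.

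**The case against.** The two rules do different jobs. The protocol's governs confirming a reading on site; Table 6 is a reporting screen. No text says they must match, so a reader who infers that the SAP contradicts the protocol goes too far. Joining a value to a change is also the SAP's usual form: heart rate and PR in Table 6, blood pressure and pulse in Table 5. At ordinary baselines Table 6 is the more sensitive rule. A man going from 405 to 436 (+31) is PCI without meeting the protocol trigger.

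A reader might also infer that a QTc signal would vanish from the report. The documents do not support that:
- Table 14.3.6.1 presents changes from baseline, and SAP 11 includes the maximum in continuous summaries. The trigger applies to scheduled ECGs, so the triggering value is in that table.
- SAP 18.3 puts repeat and unscheduled assessments in the listings, and listing 16.2.8.3.1 holds the ECG results.
- Interpretation and shift tables are planned, and an ECG change judged clinically significant is an adverse event under Protocol 8.1.4.
- The abnormal-evaluation row offers another way into the PCI outputs, although it rests on investigator judgment and is not tied to 45 msec.

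Two caveats also stand. The examples hold for QTcF and may be flagged on QTcB. The table shells are a separate document and the SAP says the planned list may change, so the absence of a count is read from the SAP text and titles.

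What survives is narrower: none of these outputs, as described, counts or flags the subjects who met the protocol's QTcF rise trigger.

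**Conclusion.** The point holds as a gap in PCI counting and flagging. On QTcF, men with baseline below 385 msec and women below 405 msec can meet the protocol's rise trigger and fall outside the QTc row. They also stay out of the PCI listing unless the ECG is rated abnormal or the row is applied to QTcB and that value qualifies. This follows from the text and needs no outside figure.

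The 500 msec arm adds almost nothing. The assumed baseline shares (about 1–62% of men, 15–95% of women) are too wide to be informative, and they must not be read as a rate of missed events. One missed subject would be 1/16 = 6.25 percentage points in a group of 16, but the documents give no basis for saying that even one is likely. This is an inexpensive improvement, not a threat to the safety conclusions.

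**What to change.** Keep every existing Table 6 row. Add one row, QTcF increase > 45 msec from baseline, mirroring the protocol's initial trigger; a row for QTcF > 500 msec is optional. Tabulate the added rows by ethnic group in table 14.3.6.4, and list the subjects who meet them, with their repeat ECGs, in listing 16.2.8.3.2. State for each QTc row whether it uses QTcF, QTcB or both.

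The cost is one or two extra rows, usually zero, from data already collected. Existing criteria and clinical management do not change.

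Separately, the Single ECG Recordings text in Protocol 7.2.2.9 gives > 4 msec from baseline as the threshold for the repeat readings and > 45 msec elsewhere. The sponsor should reconcile these figures; the point above does not depend on the outcome.

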11.5 Other Safety Variables

11.5.1 Immunogenicity Testing for Anti-Drug Antibodies

For immunogenicity, the number and percentage of subjects with ADA prevalence, ADA incidence, pre-existing ADA, treatment-induced ADA, treatment-boostered ADA, transient ADA, persistent ADA, non-neutralizing ADA, and neutralizing ADA will be summarized by ethnic group. The ADA titer and reactivity, as well as the neutralizing antibody responses will be listed.

Pre-existing ADA: a laboratory reported confirmatory positive ADA prior to treatment.

Treatment-induced ADA: ADA developed *de novo* (seroconversion) following biologic drug administration (i.e., formation of ADA any time after the initial drug administration in a subject without pre-existing ADA).

Treatment-boostered ADA: Pre-existing ADA that were boosted to a higher level following biologic drug administration (i.e., any time after the initial drug administration the ADA titer is greater than the baseline titer by 4-fold increase or more), where the fold increase will be calculated as: $\log_2(\text{post-dose ADA titer}/\text{pre-existing ADA titer})$.

ADA prevalence: The proportion of all individuals having drug-reactive antibodies (including pre-existing antibodies) at any point in time. This term is distinct from ADA incidence (see below).

ADA incidence: The proportion of the study population found to have seroconverted or boosted their pre-existing ADA during the study period. Synonymous with “treatment-emergent ADA”, ADA incidence is the sum of both treatment-induced and treatment-boostered ADA-positive subjects as a proportion of the evaluable subject population.

Transient ADA response:

- Treatment-induced ADA detected only at one sampling time point during the treatment or follow-up observation period (excluding the last sampling time point, which ought to be considered persistent unless shown to be undetectable at a later time) or
- Treatment-induced ADA detected at two or more sampling time points during the treatment (including follow-up period if any), where the first and last ADA-positive samples (irrespective of any negative samples in between) are separated by a period less than 16 weeks, and the subject’s last sampling time point is ADA-negative.

Persistent ADA response:

- Treatment-induced ADA detected at two or more sampling time points during the treatment (including follow-up period if any), where the first and last ADA-positive samples (irrespective of any negative samples in between) are separated by a period of 16 weeks or longer or

- Treatment-induced ADA incidence only in the last sampling time point of the treatment study period or at a sampling time point with less than 16 weeks before an ADA-negative last sample.

All immunogenicity summaries and data listing(s) will be based on the Safety Analysis Set. The overall ADA status (positive or negative) of each subject will be presented in the listing. Subjects meeting the criteria for ADA incidence will be considered positive for overall ADA status, and all other subjects will be considered negative for overall ADA status.

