h Thyroid function tests (TSH, T3, T4) will be collected as part of the biochemistry panel at Screening only.

i Drugs of abuse at screening, and drugs of abuse and alcohol (breath test) on Day -1 and at all out-patient visits.

j No PK or PD sample, or urine drug or alcohol screen should be collected for early discontinuation.

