4.3 Pharmacokinetic Set

The PK Set will consist of all subjects in the Safety Analysis Set who have at least 1 evaluable postdose PK concentration value. All PK analyses will be based on the PK Set.

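### Treatment-boosted ADA has two thresholds in one sentence: 4-fold by the words, 16-fold by the log2 formula

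*SAP*

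**What the plan says.** SAP 11.5.1 defines treatment-boosted ADA for subjects who were confirmed ADA-positive before dosing. A boost is recorded if at any time after dosing "the ADA titer is greater than the baseline titer by 4-fold increase or more), where the fold increase will be calculated as" log2(post-dose titer / pre-existing titer). No cut-off on the log2 scale is given and no back-transformation is mentioned.

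Treatment-induced and treatment-boosted subjects together make up ADA incidence, expressed "as a proportion of the evaluable subject population". Meeting the incidence criteria makes a subject positive for overall ADA status, and "all other subjects will be considered negative for overall ADA status". That status then stratifies the concentration summaries and figures (SAP 12.1.1), the PK parameter summaries and body-weight plots, and a sensitivity ANOVA that is run if the data allow (SAP 12.2; Table 14.2.5.6). SAP 17 lists the summaries by ADA status as an addition to the protocol analyses.

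The section also splits treatment-induced ADA into transient and persistent. The first transient bullet covers a single positive sample, "excluding the last sampling time point, which ought to be considered persistent unless shown to be undetectable at a later time". Persistent ADA needs first and last positives that "are separated by a period of 16 weeks or longer", or a positive only at the last sample, or one "at a sampling time point with less than 16 weeks before an ADA-negative last sample".

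**The concern.** The boost rule is a decision threshold, and the sentence gives two values for it. A programmer who follows the words codes a ratio of 4. One who follows the formula and compares its result with 4 codes a ratio of 16. Under the second coding, a subject with pre-existing ADA and a rise from 4-fold to under 16-fold drops out of ADA incidence, becomes negative for overall ADA status, and moves into the ADA-negative PK stratum.

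A second, smaller problem concerns subjects with no post-dose ADA result. Incidence is restricted to evaluable subjects, but overall status has only two values. The PK Set takes "all subjects in the Safety Analysis Set who have at least 1 evaluable postdose PK concentration value", so a subject with in-house PK samples and no post-dose ADA result would be analysed as ADA-negative without having been tested.

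Third, the transient and persistent definitions are not mutually exclusive. This touches only those rows of the immunogenicity summary (Table 14.3.6.5).

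**Working it through.** **Boost threshold.** The inputs are the cut-off of 4 and the formula log2(post/pre), both from SAP 11.5.1.

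| Titer ratio post/pre | log2(ratio) | Words: ratio ≥ 4 | Formula: log2 ≥ 4 | log2 ≥ 2 |
|---|---|---|---|---|
| 2 | 1 | no | no | no |
| 4 | 2 | yes | no | yes |
| 8 | 3 | yes | no | yes |
| 16 | 4 | yes | yes | yes |
| 32 | 5 | yes | yes | yes |

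The formula does not reproduce the stated 4-fold threshold, because the smallest ratio that reaches 4 is 2^4 = 16. The two rules disagree for ratios from 4 to under 16. If titers come from a two-fold dilution series (an assumption; the documents do not say), these are the ratios 4 and 8. Reading the words as four times the baseline added to the baseline gives a ratio of 5, and log2(5) = 2.32, which does not reconcile them either. A cut-off of 2 on the log2 scale matches the words exactly.

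Nothing elsewhere settles it. Protocol 7.2.5 has no boost definition, SAP 17 does not mention the point, and SAP 1 places the table shells in a separate document.

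**Size per subject.** With 16 evaluable subjects in a group, 1/16 = 6.25 percentage points of incidence. With 12, the expected number of completers, 1/12 = 8.3 points.

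**Transient and persistent.** Protocol Table 3 lists 5 ADA samples. Protocol 7.2.5 puts one before dosing, leaving 5 − 1 = 4 post-dose samples and 2^4 − 1 = 15 possible patterns with at least one positive. The ADA row of Protocol Table 2 is not legible in the available text, so visit days were not assumed: all 35 choices of 3 visits from Days 7 to 84, each with Day 112, were enumerated. The widest span uses the extreme visit windows, Day 6 to Day 115: 115 − 6 = 109 days, or 15.6 weeks. Sixteen weeks is 112 days, so the limb requiring 16 weeks or longer cannot be met on scheduled visits. All 35 choices give the same counts:

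| Reading | Persistent only | Transient only | Both | Neither |
|---|---|---|---|---|
| *Only* carries to the second limb of persistent bullet 2; parenthetical on the last sample not used | 1 | 4 | 3 | 7 |
| Same, parenthetical used | 8 | 4 | 3 | 0 |
| *Only* does not carry; parenthetical not used | 1 | 0 | 7 | 7 |
| Same, parenthetical used | 8 | 0 | 7 | 0 |

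The 3 patterns meeting both definitions are a single positive at one of the first three samples followed by a negative last sample. The 7 meeting neither have a positive last sample plus at least one earlier positive; they are persistent only through the parenthetical, which sits inside the transient definition. These are logical patterns, not expected numbers of subjects.

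**The case against.** The intent can be read from the words. The criterion is stated on the titer itself, and log2 may be only a working scale on which 4-fold equals 2. On that view this is a mislabelled formula, correctable in one line. The reading is sensible, but the SAP does not state it, and the sentence says how the fold increase is to be calculated.

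The reach is also narrow. The rule matters only for subjects with pre-existing ADA and a rise in the disputed range, who may number zero. Prevalence, pre-existing ADA and treatment-induced ADA do not use it. The main ethnic-group ANOVA does not use ADA status, no hypothesis is tested, the stratified ANOVA is conditional on the data, and titers are listed, so a reader could reclassify. The 8.3-point figure needs a group of only 12 evaluable subjects, whereas immunogenicity uses the Safety Analysis Set, planned at 16 per group. All of this stands and limits the weight of the point. It does not remove the contradiction, and reclassifying from listings does not replace one prespecified rule.

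Untested subjects should be uncommon. Footnote j to Protocol Table 1 reads "No PK or PD sample, or urine drug or alcohol screen should be collected for early discontinuation" and so leaves ADA sampling in place, and Protocol 4.5 asks discontinued subjects to attend the Day 112 visit where possible. That too stands; what remains is a missing category.

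Of the transient and persistent faults, the unreachable 16-week limb misclassifies nobody, and the parenthetical resolves the patterns that meet neither definition. The overlap for a single early positive is real, but it does not affect overall ADA status.

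**Conclusion.** The concern holds. The boost threshold is 4-fold by the words and 16-fold by the formula applied literally, and neither document reconciles them. Rises from 4-fold to under 16-fold change class between the two readings, which carries through to ADA incidence, overall ADA status and every PK output stratified by that status. The primary ethnic comparison is not affected. The number of subjects involved cannot be estimated because the documents give no pre-existing ADA rate; the percentage-point figures are per affected subject.

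The absence of a not-evaluable class is a secondary gap. It affects the ADA-negative PK strata, by one untested subject at a time, and leaves the incidence denominator unchanged; no count is claimed. The transient/persistent overlap is minor and confined to descriptive rows. The point should be fixed, chiefly for the boost threshold.

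**What to change.** Before database lock, amend SAP 11.5.1 as follows:

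- Define treatment-boosted ADA as a post-dose to pre-existing titer ratio of at least 4, or equivalently a log2 ratio of at least 2, and state only one cut-off for each scale used.
- Classify subjects with no post-dose ADA result as not evaluable for overall ADA status, in line with the incidence denominator, and keep them out of the ADA-stratified PK summaries.
- Make transient and persistent mutually exclusive. Move the rule on a positive last sample into the persistent definition, assign a single early positive with a negative last sample to one class, and state whether *only* governs both limbs of the second persistent bullet.

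The cost is SAP wording and derivation code. No new samples or assays are needed.

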12.2 Statistical Analysis of Pharmacokinetic Parameters

Descriptive statistical analysis of PK parameters will be based on the PK Set. The plasma PK parameters of lanadelumab will be summarized by ethnic group, and separately by ethnic group and overall ADA status. Summaries will include: n, arithmetic mean, SD, %CV, median, minimum, maximum, geometric mean, and %CV of geometric mean. In addition, 95% confidence intervals (CIs) for PK parameters will be provided. Listing of individual plasma PK parameters of lanadelumab will be provided based on the Safety Analysis Set. Individual (observed) and body weight-adjusted PK parameters (y-axis) versus body weight (x-axis) by ethnic group and overall ADA status will be presented in figures on both linear and semi-logarithmic scales for AUC_{0-last} , $AUC_{0-\infty}$, C_{max} , CL/F, and V_z/F .

Following ln-transformation, the PK parameters C_{max} , AUC_{0-last} , and $AUC_{0-\infty}$, will be analyzed using an analysis of variance (ANOVA) model, for estimation purposes. No formal hypothesis testing will be performed. The model will include ethnic group as a fixed effect. Point estimates and their associated 90% CIs will be constructed for the differences in the ln-transformed parameters. The point estimates and their associated 90% CIs will be then back-transformed to provide point estimates for the ratio (Japanese Subjects/Caucasian Subjects) of geometric least squares means and associated 90% CIs on the original scale.

To assess the impact of overall ADA status on the ethnic group comparison, if data permits, a sensitivity analysis will be performed by repeating the above ANOVA analyses by overall ADA status.

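### Overall ADA status records unknown results and pre-existing, unboosted antibody as negative, so the ADA-negative stratum of the supplementary PK analyses is not clean

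*SAP*

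**What the plan says.** SAP Section 11.5.1 sets the rule in two halves. The first fixes who is positive: "Subjects meeting the criteria for ADA incidence will be considered positive for overall ADA status". The second covers everybody else: "all other subjects will be considered negative for overall ADA status". The status has two levels and is given to everyone: "The overall ADA status (positive or negative) of each subject will be presented in the listing". That listing is based on the Safety Analysis Set.

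The same section defines the terms that feed the rule. Pre-existing ADA is "a laboratory reported confirmatory positive ADA prior to treatment". ADA incidence is "the sum of both treatment-induced and treatment-boostered ADA-positive subjects as a proportion of the evaluable subject population". ADA prevalence is "The proportion of all individuals having drug-reactive antibodies (including pre-existing antibodies) at any point in time". The evaluable population is not defined, and the idea of evaluability is not carried into the status rule.

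SAP Sections 12.1.1 and 12.2 use the status to split the PK concentration and parameter summaries and the figures, alongside summaries by ethnic group alone. Section 12.2 also repeats the ethnic-group ANOVA by status, where the data allow. Its purpose is given as: "To assess the impact of overall ADA status on the ethnic group comparison".

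**The concern.** A status that is useful for reporting treatment-emergent antibody is reused as a PK stratifier. For that second use, the negative stratum should hold subjects in whom antibody was looked for after dosing and never confirmed. Under the rule as written it also takes in two other kinds of subject:

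- **Unknown status.** A subject with no post-dose ADA result cannot meet incidence and so becomes negative by default. Missing data are recorded as a finding.
- **Known drug-reactive antibody.** A subject with a confirmed positive before dosing whose titer does not rise enough to count as boosted is also negative.

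At stake is the stratified sensitivity analysis. Its reference group is the negative stratum. If antibody affects exposure and affected subjects sit in that group, the contrast between strata is blurred. If they sit in one ethnic group only, the Japanese/Caucasian ratio within the stratum moves.

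**Working it through.** **1. The plan's own figure.** SAP Section 2.5 plans 32 subjects and 25% dropout. 32 × (1 - 0.25) = 24 completers and 16 × 0.75 = 12 per group, as stated. That leaves 8 expected dropouts.

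**2. The rule applied to each possible ADA profile.**

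| Profile | Meets incidence? | Overall status |
|---|---|---|
| No ADA at any time, post-dose result available | No | Negative |
| Treatment-induced | Yes | Positive |
| Pre-existing, boosted | Yes | Positive |
| Pre-existing, not boosted | No | Negative |
| No post-dose ADA result | Cannot be shown | Negative |

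The last two rows are the problem. No other section overrides them.

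**3. Can these subjects reach the PK strata?** Yes. The PK Set (SAP Section 4.3) requires dosing and one evaluable post-dose concentration. It requires no ADA result.

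**4. Which outputs use the status?** Tables 14.2.5.2, 14.2.5.4 and 14.2.5.6 and Figure 14.2.5.2 carry it in their titles. Section 12.2 also plans the body-weight plots by status, and the PK listings show it. Tables 14.2.5.1, 14.2.5.3 and 14.2.5.5 and Figure 14.2.5.1 do not use it. The main ANOVA has ethnic group as its only effect.

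**5. Size, by assumption.** Let R be the AUC of a mislabelled subject relative to true negatives, and n the size of one ethnic group's negative stratum, including that subject. One such subject multiplies the geometric mean by R^(1/n), a shift of exp(ln R / n) - 1.

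| R (assumed) | n = 16 | n = 12 |
|---|---|---|
| 0.7 | -2.2% | -2.9% |
| 0.5 | -4.2% | -5.6% |
| 0.3 | -7.2% | -9.5% |

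With R = 0.5 and n = 16, the factor for one, two or four subjects is 0.958, 0.917 or 0.841. One such subject in the Japanese group multiplies the stratum's ratio by 0.958. One in the Caucasian group multiplies it by 1/0.958 = 1.044. One in each group, with equal n and R, cancels.

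**6. Scale.** The 90% CI for the ratio extends by a factor exp(t × √ln(1 + CV²) × √(2/n)), with t the 95th percentile on 2n - 2 degrees of freedom. At an assumed CV of 30% this is 1.19 for 16 per group and 1.23 for 12. For CVs of 20% to 40% it runs from 1.13 to 1.26 (16 per group) and from 1.15 to 1.31 (12 per group).

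**7. How many such subjects?** The documents do not say. If the pre-existing rate were 1%, 3%, 5% or 10%, the chance of at least one among 32, 1 - (1 - p)^32, would be 0.28, 0.62, 0.81 or 0.97; only those not boosted are mislabelled. Of the 8 expected dropouts, anywhere from 0 to 8 could lack a post-dose ADA result. Protocol Table 3 lists five ADA samples. Section 7.2.5 places one before dosing, which leaves four afterwards. Their days could not be checked, because the ADA row of Table 2 is missing from the text available here.

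**The case against.** The strongest reply is that the rule is a deliberate, prespecified choice. Section 11.5.1 separates prevalence from incidence in so many words, equates incidence with treatment-emergent ADA, and ties the overall status to it. A reader might infer that the SAP contradicts itself because a subject can count towards prevalence and still be labelled negative. It does not: these are different measures, and an evaluable denominator for a proportion does not conflict with a subject-level label. That part of the reply stands. It does not supply the missing level for unknown status, nor does it make a treatment-emergent label a suitable definition of antibody-free.

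The plan also limits the no-sample case. Protocol Table 1 marks ADA testing in the out-patient/early-discontinuation column, and the footnote that withholds samples at early discontinuation names PK, PD and drug and alcohol screens, not ADA. Protocol Section 4.5 asks for the withdrawal evaluations and, where possible, the Day 112 visit. So the 25% dropout figure must not be read as 25% without a post-dose ADA result. This also stands, although collection in leavers is best effort.

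Finally, the information needed to spot an affected subject is reported. Section 11.5.1 summarises pre-existing ADA and prevalence and lists titers; Table 14.3.6.6 tabulates positives by timepoint; Listing 16.2.8.4 gives the individual results. With 32 subjects, reclassification by hand is feasible. It would not correct the planned stratified tables or ANOVA, and it would be done after the PK results were known.

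**Conclusion.** The concern holds in a limited form. The two-level rule places subjects of unknown ADA status and subjects with confirmed pre-existing, unboosted antibody in the ADA-negative stratum, and the ADA-stratified PK outputs inherit that.

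A reader might go further and infer that the PK results in general, or the primary objective, are compromised. The documents do not support this: the unstratified summaries and the main ethnic-group ANOVA never use the status, and no hypothesis is tested.

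Nor is any particular bias established. The shift of -4.2% among 16, or -5.6% among 12, rests on one mislabelled subject with an assumed halving of AUC. The documents report no PK effect of pre-existing, unboosted antibody. A single such subject is well inside the precision of the ratio at the assumed 30% CV, and with none the effect is zero. For subjects with no post-dose result no size can be given, since their true status is unknown.

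The point should be corrected because it affects the reference group of a prespecified sensitivity analysis and costs little to put right before the data are seen.

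**What to change.** In SAP Section 11.5.1, keep treatment-emergent ADA as the definition of incidence and of a positive overall status. For the PK strata, specify:

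- **Negative:** no confirmed ADA at any time, with at least one evaluable post-dose ADA result.
- **Not evaluable:** no post-dose ADA result; listed, but left out of the ADA-stratified summaries and ANOVA.
- **Pre-existing, not boosted:** shown as its own category. Pooling it with the positives is debatable, because it would mix unboosted baseline reactivity with treatment-emergent response; pooling it with the negatives is the present problem.

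Define what makes a subject evaluable for ADA, and carry the new levels into Sections 12.1.1 and 12.2 and the table shells.

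The cost is a paragraph of SAP text and one derived variable. The ADA-negative stratum may lose one or a few subjects, and the separate category may be too small to summarise beyond a listing.
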